## 9.3 Statistical Analysis Methods

### 9.3.1 Analysis Plan

The Kaplan-Meier method will be used to estimate 2-year EFS from the end of Induction I along with 95% log-minus-log transformed confidence limits separately for HR and SR patients at end of Induction I. To compare the Kaplan Meier estimate of 2-year EFS (KM2) with fixed values, we will use the test statistic  $\frac{\ln(-\ln(\text{KM2})) - \ln(-\ln(0.935))}{\text{Estimated SD} [\ln(-\ln(\text{KM2}))]}$  for SR and  $\frac{\ln(-\ln(\text{KM2})) - \ln(-\ln(0.76))}{\text{Estimated SD} [\ln(-\ln(\text{KM2}))]}$  for HR patients and compare these with a standard normal distribution.

\* Updated with Amendment #4A

AAML1531 was temporarily closed to accrual on October 1, 2018, due to results of an interim analysis identifying a significantly lower EFS for SR patients than that expected based on comparative data from AAML0431. Post-Induction I treatment on the SR Arm A was permanently closed on October 18, 2018. All patients enrolled prior to amendment #4A who were assigned to the SR arm were to be taken off protocol therapy but may stay on study. These SR patients enrolled prior to amendment #4A who are taken off protocol therapy due to the closure of treatment on the SR arm will be censored in future EFS analysis at the time they were taken off protocol therapy. Patients enrolled after amendment #4A who are assigned to the SR arm will be removed from study and continue treatment off protocol per standard of care. No further data will be collected on these patients.

### 9.3.2 Interim Monitoring

#### Standard Risk Patients - lack of efficacy

Monitoring for insufficient EFS from the end of Induction I of the treatment for SR patients on this study will utilize monitoring based on the Lan-DeMets criterion with an  $\alpha$ -spending function  $\alpha t^2$  (truncated at 3 standard deviations) and 10% type I error. Formal monitoring analyses of differences in the number of EFS events observed in the available follow-up and the expected number of events under the null hypothesis for the available follow-up will be performed after approximately 50% of the expected number of EFS events have been observed (after 8 of 16 total events for SR) which is anticipated to occur after approximately 156 patients are assigned to the SR arm. For interim monitoring, we will conduct a Woolson one-sample log rank test for SR to compare the observed EFS with AAML0431 EFS for patients who continue to Induction II treated as fixed and known. EFS for AAML0431 will be characterized by the following separate cure model for SR patients:

$$S(t) = 0.905 + (0.095) * \exp(-0.00127 * t) \quad t \text{ measured in days}$$

A p-value that is less than the boundary value of 0.025 for 50% information time will result in rejection of the hypothesis and the possible suspension of enrollment to the stratum will be identified to the COG DSMC.

\* Updated with Amendment #4A

Interim monitoring has been completed for standard risk patients.

High Risk Patients - efficacy

Monitoring for improvement in EFS from the end of Induction I of the treatment for HR patients on this study will utilize monitoring based on the Lan-DeMets criterion with an  $\alpha$ -spending function  $\alpha t^2$  (truncated at 3 standard deviations) and 10% type I error. Formal monitoring analyses of differences in the number of EFS events observed in the available follow-up and the expected number of events under the null hypothesis for the available follow-up will be performed after approximately 50% of the expected number of EFS events have been observed (5 to 6 of 11 total events for HR) which is anticipated to occur after approximately 16-21 patients are assigned to the HR arm. For interim monitoring, we will conduct a Woolson one-sample log rank test for HR patients to compare the observed EFS with AAML0431 EFS for patients who continue to Induction II treated as fixed and known. EFS for AAML0431 will be characterized by the following cure model for HR patients:

$$S(t) = 0.75 + (0.25) * \exp(-0.0037 * t) \text{ t measured in days.}$$

A p-value that is less than the boundary value of 0.025 for 50% information time will result in rejection of the hypothesis and the possible suspension of enrollment to the stratum will be identified to the COG DSMC.

High Risk Patients – toxic deaths

No toxic deaths were observed on AAML0431. Possible suspension of enrollment to the High Risk stratum will be considered if 3 or more toxic deaths, i.e. deaths as first event while on protocol therapy or within 30 days of going off protocol therapy, are observed on the High Risk arm. For a true toxic death rate of 2%, there is a 4.9% chance of observing 3 or more toxic deaths. For a true toxic death rate of 10%, there is a 79.1% chance of observing 3 or more toxic deaths.

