## 2.9

### **Interim Analysis of Patients Treated on the Standard Risk Arm**

According to the study analysis plan, an interim analysis of treatment outcomes for lack of efficacy on the Standard Risk (SR) arm (Arm A) was performed after 50% of the expected number of EFS events had been observed (after 8 of 16 events). Based on a model generated using data of SR patients in the historical control (predecessor study AAML0431) and the amount of follow-up available at the time of data cut off (30 June 2018), 2.4 EFS events were expected in SR patients compared to 8 EFS events observed. The projected 2-year EFS for SR patients on AAML1531 is significantly lower than on AAML0431 (85.6% compared to 93.5%, p 0.0002). As of October 5, 2018, 9 of 109 SR patients on AAML1531 have experienced a relapse at 136 to 327 days after study entry. Four of these relapses occurred on therapy (1 during Intensification I, 3 during Intensification II) and 5 during the first 6 months of follow up after completion of protocol therapy. Of the 9 relapsed SR patients, 8 have died.

These data show lack of sufficient efficacy of AAML1531 protocol therapy for SR patients. Based on this information, post-Induction I treatment on the SR Arm A of AAML1531 was permanently closed.

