### 9.2 Patient Accrual and Expected Duration of Trial

AAML1531 will be compared against a fixed 2-year EFS of 93.5% for SR patients and 76% for HR patients which were observed for comparable patients treated on the prior COG study of DS AML patients (AAML0431). For SR patients, assuming a null EFS of 93.5% at 2 years, there is 95% power to detect an alternative EFS of 87% at 2 years with 1-sided testing at the 10% level of statistical significance if there are 200 SR patients who continue to Induction II. For HR patients, assuming a null EFS of 76% at 2 years, there is 80% power to detect an alternative EFS of 88% at 2 years with 1-sided testing at the 10% level of statistical significance if there are 41 high risk patients who continue to Induction II. The necessary sample size was computed using a binomial test. The final analysis of EFS will occur after a minimum of 2 years after the last patient is enrolled.

\* Replaced with Amendment #6

Up to 3% of patients enrolled are expected to be found ineligible, up to 3% are expected to go off protocol therapy at the end of Induction I, and approximately 83% of patients are expected to be SR. Therefore, enrollment of up to 256 patients will be required to assure that there are 200 SR patients who continue to Induction II and there are 41 HR patients continue to Induction II. Based on an accrual estimate of 60 patients per year, accrual of 256 patients is expected to be completed in approximately 4.3 years.

\* Updated with Amendment #4A

As of October 22, 2018, 26 of the 143 patients enrolled are HR patients who continued to Induction II. Up to 3% of patients enrolled are expected to be found ineligible, up to 3% are expected to go off protocol therapy at the end of Induction I, and approximately 83% of patients are expected to be SR. Therefore, enrollment of up to 256 patients will be required to assure that there are 41 HR patients who continue to Induction II. Based on an accrual estimate of 60 patients per year, accrual of an additional 113 patients is expected to be completed in approximately 2 years.

\* Updated with Amendment #6

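### The interim null curves give 94.3% (SR) and 76.7% (HR) at 2 years, not the fixed 93.5% and 76% of the design and final test, and section 2.9 does not say which curve lies behind its p-value

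*Combined protocol and SAP*

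**What the plan says.** Section 9.2 sets the benchmarks: "AAML1531 will be compared against a fixed 2-year EFS of 93.5% for SR patients and 76% for HR patients". It presents both as values observed in comparable AAML0431 patients. Section 9.3.1 builds the final test statistics on 0.935 and 0.76.

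Section 9.3.2 sets the interim test as a Woolson one-sample log-rank test against the AAML0431 curve, taken as fixed and known:

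- SR, lack of efficacy: "EFS for AAML0431 will be characterized by the following separate cure model for SR patients", namely S(t) = 0.905 + 0.095·exp(−0.00127t), t in days.
- HR, efficacy: "EFS for AAML0431 will be characterized by the following cure model for HR patients", namely S(t) = 0.75 + 0.25·exp(−0.0037t).

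The boundary at 50% information is p < 0.025. The SR look was planned at 8 of 16 events.

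Section 2.9 reports the SR look at the 30 June 2018 cut-off: "2.4 EFS events were expected in SR patients compared to 8 EFS events observed". It then sets a projected 2-year EFS of 85.6% beside 93.5%, with p 0.0002. It says the expected count came from a model of AAML0431 SR data but does not print the equation.

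**The concern.** The benchmarks and the curves describe the same historical patients, and both are treated as known without error. They should agree at 2 years, and they do not. In each stratum the curve lies above the benchmark, so the interim and final analyses test different nulls.

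The practical consequence is in section 2.9. A reader will take p 0.0002 as a test of 85.6% against 93.5%. If the model used there is the 9.3.2 equation, the comparator reached 94.3% at 2 years. That p-value is the printed evidence for permanently closing a treatment arm in a paediatric trial, so its comparator should be clear. The HR curve matters too: the text marks interim monitoring as completed for SR but not for HR.

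**Working it through.** **Inputs.** Benchmarks 0.935 and 0.76, 200 SR patients, 4.3 years of accrual and at least 2 years of follow-up (9.2); both curves and the boundary (9.3.2); 8 observed and 2.4 expected events, p 0.0002 (2.9). Individual follow-up and the number of SR patients at the June 2018 cut are not given. Section 2.9 gives 109 SR patients as of 5 October 2018; I assume 80–109 at the cut, with follow-up uniform from 0 to T.

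**1. The plan's own figures reproduce.**
- z = (8 − 2.4)/√2.4 = 3.61. One-sided p = 0.00015, which rounds to 0.0002; two-sided would be 0.0003.
- Boundary: 0.10 × 0.5² = 0.025.
- Total SR events from the printed curve, 200 patients, uniform accrual: 15.7 (averaging 1 − S) or 16.4 (averaging −ln S), against 16 planned.

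**2. The curves at day 730.**
- SR: exp(−0.00127 × 730) = 0.3957, so S = 0.905 + 0.095 × 0.3957 = 0.9426. The gap is 0.76 points. The curve reaches 93.5% only at about day 908.
- HR: exp(−0.0037 × 730) = 0.0671, so S = 0.75 + 0.25 × 0.0671 = 0.7668. The gap is 0.68 points.
- Cumulative hazard, SR: −ln 0.9426 = 0.0591 against −ln 0.935 = 0.0672, which is 12% lower. HR: 0.2655 against 0.2744, 3% lower.
- Moving the time origin by one Induction I cycle (34 days) gives 94.1% for SR, so that does not explain the gap.

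**3. SR curves that do pass through 93.5%.**
- Plateau changed, rate kept: 0.065/(1 − 0.3957) = 0.1076, so the plateau is 0.892.
- Rate changed, plateau kept: exp(−730r) = 1 − 0.065/0.095 = 0.3158, so r = 0.00158 per day.
- Constant hazard, to test the effect of shape: 0.0672/730 = 0.0000921 per day.

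**4. Effect on the interim.** T is chosen so that the printed curve gives 2.4 expected events: N × mean of −ln S(u) over 0 to T = 2.4. This makes T about 625 days for N = 80 and 428 days for N = 109. Each alternative curve is then averaged over the same follow-up.

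| SR null curve | Expected events E | One-sided p, z = (8 − E)/√E |
|---|---|---|
| As printed | 2.4 | 0.00015 |
| Plateau 0.892 | 2.72 | 0.0007 |
| Rate 0.00158/day | 2.83–2.88 | 0.0011–0.0013 |
| Constant hazard | 2.15–2.30 | 0.00003–0.00009 |

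Exact Poisson tails for the two re-anchored cure curves are about 0.007–0.009, also below 0.025. To lose significance in the normal form, E would have to reach about 4.05. Under proportional scaling that is a 2-year null of 0.9426^(4.05/2.4) ≈ 90.5%.

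**5. Effect on the boundary.** Suppose 8 SR events are expected at the look. The boundary is crossed above 8 + 1.96√8 = 13.54 events. If the truth is the plateau-0.892 curve, the mean is about 8 × 1.135 = 9.08, and (13.54 − 9.08)/√9.08 = 1.48. The chance of crossing is about 7% instead of 2.5%, both in normal approximation.

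**The case against.** The strongest defence is that the curve is the interim null. Section 9.3.2 prespecifies and prints it, and nothing in the plan requires it to equal 93.5% at day 730. It reproduces the 16 planned events, and the p-value and boundary also check. This stands. A reader might infer that the 2.4 expected events and p 0.0002 tested the wrong null; the documents do not support that.

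A second defence concerns direction. A one-sample log-rank test with short follow-up depends on the early part of the curve, not its 2-year value. As the constant-hazard row shows, a curve through exactly 93.5% can give fewer expected events and a smaller p. Constant hazard is not offered as the true shape, but it shows that the benchmark alone does not fix the sign. A reader might infer that the evidence for closure was exaggerated; that too is not established.

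Third, the gap is small. Using the 125 MRD-negative AAML0431 patients in section 2.10.2.2, a rough binomial standard error is √(0.935 × 0.065/125) = 2.2 points, and 0.76 points is about one patient. A smooth fit may miss an empirical estimate by this much. That makes the gap understandable, but it does not remove the need to state it when both figures are treated as known.

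Finally, replacing a completed prespecified test after its result is known would be poor practice. That stands and shapes the fix.

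**Conclusion.** The inconsistency is certain: 94.3% against 93.5% for SR and 76.7% against 76% for HR, unexplained in the documents. That the figures in 2.9 came from the printed 9.3.2 curve is an inference: it is the only SR model in the documents, but 2.9 does not identify it.

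Keeping the plan's cure form and passing it through 93.5% gives about 2.7–2.9 expected events and a one-sided p of about 0.0007–0.0013, roughly 5 to 8 times the 0.00015 from the printed figures. The range rests on the assumed uniform follow-up in 80–109 patients, and the direction depends on curve shape. The 0.025 boundary is crossed under every curve examined, so the closure of Arm A is not in question. For HR the look is for improvement, so with the plan's own curve shape a null set slightly high makes crossing harder, not easier.

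This is a consistency and reporting correction.

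**What to change.** 1. Compare both printed curves with the AAML0431 Kaplan-Meier estimates and reconcile them with 93.5% and 76%, or state why they differ.
2. Keep the prespecified SR interim result. Add a re-run on the 30 June 2018 cut, labelled as a sensitivity analysis, using the AAML0431 Kaplan-Meier curve or a cure curve through 93.5%, for example S(t) = 0.892 + 0.108·exp(−0.00127t).
3. In 2.9, state which curve gave 2.4 and 0.0002, its 2-year value, and that the p-value is one-sided if that is confirmed. Separate it from the descriptive comparison of 85.6% with 93.5%.
4. For any HR look not yet done, use a reconciled curve. One that keeps the rate and passes through 76% is S(t) = 0.743 + 0.257·exp(−0.0037t), from 1 − 0.24/(1 − 0.0671); the AAML0431 data should decide the shape.

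The cost is one re-run on existing data and a few sentences. No decision already taken needs to change.

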As of August 25, 2020, 32 of the 222 patients enrolled are HR patients who continued to Induction II and 5 patients have not been risk classified yet. Assuming 10% of enrolled patients will be HR, enrollment of up to 312 patients will be required to assure that there are 41 HR patients who continue to Induction II. Based on an accrual estimate of 60 patients per year, accrual of an additional 90 patients is expected to be completed in approximately 1.5 years.

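### The high-risk efficacy look starts at 5–6 observed events, a count at which its 0.025 boundary cannot be reached at the planned 16–21 patients or at any number below the full 41

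*Combined protocol and SAP*

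**What the plan says.** Section 9.3.2, under High Risk Patients – efficacy, states its purpose as "Monitoring for improvement in EFS from the end of Induction I of the treatment for HR patients on this study". It uses the spending function αt² with a 10% type I error. The look comes "after approximately 50% of the expected number of EFS events have been observed (5 to 6 of 11 total events for HR"). For the size of the arm at that point, the section gives this forecast: "which is anticipated to occur after approximately 16-21 patients are assigned to the HR arm". The test is Woolson's one-sample log-rank against S(t) = 0.75 + 0.25·exp(−0.0037t), t in days. The decision rule is: "A p-value that is less than the boundary value of 0.025 for 50% information time will result in rejection of the hypothesis". A crossing is then identified to the DSMC as a possible suspension of enrollment. No other HR efficacy trigger is given, whether by calendar time, patient number or expected events.

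The standard-risk (SR) lack-of-efficacy look in the same section has the same trigger wording. Section 2.9 shows how that wording was applied: the look was held at 8 of 16 events, when "2.4 EFS events were expected in SR patients compared to 8 EFS events observed". The Amendment 4A note says "Interim monitoring has been completed for standard risk patients"; there is no such statement for HR. Section 9.2 reports: "As of August 25, 2020, 32 of the 222 patients enrolled are HR patients who continued to Induction II".

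**The concern.** A trigger on observed events suits a harm look, because events that arrive early are themselves the signal. In a look for benefit the signal is that events fail to arrive. Waiting for 5 or 6 of them means the expected count must already be about twice as large before the boundary can be crossed, and the cure-model null caps the expected count at a low value per patient.

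If that cap lies below the required count, the plan describes to the monitoring committee an alpha-spending efficacy look that cannot reject. The better the regimen works, the later the look comes, and it may never come.

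**Working it through.** **Inputs.** From section 9.3.2: the HR null curve, one-sided boundary 0.025, trigger of 5–6 events out of 11, and 16–21 patients. From section 9.2: 41 HR patients, one-sided 10% level, alternative 88% at 2 years, 60 enrolled per year, HR fraction 10% (Amendment 6) or 17% (100% − 83% SR), and 32 HR patients in August 2020.

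**The plan's own figures reproduce.** Boundary: 0.10 × 0.5² = 0.025. Total events: 41 × [−ln S(730)] = 41 × 0.2655 = 10.9, that is, 11.

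**Required expected count.** Woolson's statistic is Z = (O − E)/√E, where E sums −ln S(t) over patients. Rejecting for benefit needs (E − O)/√E > 1.96, so √E > [1.96 + √(1.96² + 4·O)]/2:
- O = 5: E > 11.71
- O = 6: E > 13.09

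**Ceiling.** S(t) never falls below 0.75, so a patient adds at most −ln 0.75 = 0.2877 even with unlimited follow-up. The boundary therefore needs 11.71/0.2877 = 40.7 patients for 5 events and 13.09/0.2877 = 45.5 for 6, which is more than the arm.

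| HR patients | Maximum E | Best p, 5 events | Best p, 6 events |
|---|---|---|---|
| 16 | 4.60 | 0.57 | 0.74 |
| 21 | 6.04 | 0.34 | 0.49 |
| 32 | 9.21 | 0.083 | 0.145 |
| 40 | 11.51 | 0.0275 | 0.052 |
| 41 | 11.79 | 0.0239 | 0.046 |

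At 16 patients, 5 events already exceed the maximum E, so the statistic points the wrong way. An exact Poisson test gives the same threshold for 5 events (0.0276 at 40 patients, 0.0231 at 41). The single exception, 5 events in all 41 patients, needs 41 × [−ln S(t)] = 11.71, which gives t = 1,360 days (3.7 years) for every patient, including the five with events. If those five fail at 90 to 365 days and the rest are followed without limit, p is 0.040 to 0.029.

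**Simulation of the rule as written.** Assumptions: 41 patients; 6 HR patients per year (60 × 10%) or 10.2 (60 × 17%); true 2-year EFS 76.7% (the model null), 88%, 92% or 95%; follow-up to two years after last entry. There were 0 crossings in 160,000 trials, and no p-value was below 0.027. At 88% EFS (41 × 0.12 = 4.9 events by two years) the fifth event occurred in about 61% of trials. Under the null it came at a median of 23–26 patients.

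**The 16–21 range.** At the 21st entry the null-expected count is 4.15 (counting by 1 − S) or 4.68 (by cumulative hazard) at 6 per year, and 3.48 or 3.86 at 10.2 per year. Reaching 5–6 takes about 22–31 patients. The stated range fits only if every patient is already at the plateau (5/0.2877 = 17.4; 6/0.2877 = 20.9).

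**The case against.** The strongest reply is that the trigger is loose wording for expected events, since 16–21 patients is close to 5–6 null-expected events at the plateau. But the text says the events have been observed, and the identically worded SR rule was run on observed events. The expected-event reading also gives little. At E = 5.5 only 0 events cross (1 event gives p = 0.0275), and at E = 6 one event does (p = 0.021). With the hazard ratio implied by 88%, ln 0.88/ln 0.7668 = 0.48, the chance of 0 events at E = 5.5 is about exp(−0.48 × 5.5) = 7%.

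Second, the figure of 41 depends on variance E. With variance O the minimum is 33 patients (5 events) or 38 (6 events); with (O + E)/2 it is 37 or 42. That is correct, but the plan names Woolson's test, which uses E, and both 16–21 and 32 patients are impossible under every variant.

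Third, the harm is limited, and this stands. A look that cannot reject is conservative, and a crossing leads only to a possible suspension being raised with the DSMC. Section 9.2 shows at most 41 − 32 = 9 HR patients still to enter after August 2020.

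Fourth, an HR look may already have been held, since 26 HR patients had continued to Induction II by October 2018. The documents do not say, so the rule stands as current text.

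**Conclusion.** The concern holds. As written, the HR efficacy look cannot cross its boundary at the planned 16–21 patients, at the 32 reported in August 2020, or at any number below 41. At 41 it can cross only with exactly 5 events and follow-up close to the model limit. These are mathematical ceilings that need no accrual assumption; they rest on the stated null curve, Woolson's variance and the fixed 0.025. The 39% of trials with no look at all under 88% EFS comes from simulation and depends on the assumed accrual.

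The final Kaplan-Meier test and its type I error are not harmed. What is lost is the early look and an accurate account of it to the DSMC. This should be fixed, but it does not threaten the primary conclusion. The mismatch of 16–21 patients with 5–6 expected events is secondary.

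**What to change.** In section 9.3.2, HR efficacy, choose one:

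- **(a)** Delete the look and state that the full one-sided 10% is kept for the final test. The cost is giving up early stopping for efficacy.
- **(b)** Define information as null-expected events: the sum of −ln S₀(t) over HR patients, each followed to event or data cut-off, out of about 11. Hold the look at the fraction t actually reached, use 0.10·t² in place of the fixed 0.025, and state the level left for the final test.

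Illustration of (b) at August 2020. Entry dates are not in the documents, so assume 26 patients entered uniformly over the 2.0–2.9 years before 22 October 2018 and 6 over the next 673 days. The expected count is then about 7.3 (by 1 − S, the null average) to 8.3 (cumulative hazard with no events). This gives t = 0.66–0.76 and a boundary of 0.044–0.058. At E = 7.3, 2 events cross (p = 0.025) and 3 do not (0.056). At E = 8.3, 3 events cross (0.033) and 4 do not (0.068). Simulated crossing probability is about 45% at 88% EFS and 4% under the null.

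The final nominal level falls from 10% to about 8.4–8.7%. That figure assumes correlation √t between the two tests, as for a single log-rank process. The final test is a Kaplan-Meier comparison at 2 years, so the sponsor should compute the level for that pair of tests before fixing it.

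Under either option, say whether an HR look has been held, as is done for SR, and delete the 16–21 range or restate it with its accrual assumption. Only statistical wording changes. Whether HR also needs a rule for poor EFS is a separate design choice and not part of this correction.
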